7.4. Subgroup Analyses

Subgroup Analysis
Endpoints

Repeat specified analyses/displays for:
 
 • Study Population • Efficacy • Safety 
Output for subgroup analysis indicated in Section 10.8.8

Model Specification

 • Analysis will be performed 'by' each subgroup separately. Please refer to main endpoint model for model specification.
Model Checking & Diagnostics

 • As per main endpoint
Model Results Presentation

 • As per main endpoint

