2. SUMMARY OF KEY PROTOCOL INFORMATION

2.1. Changes to the Protocol Defined Statistical Analysis Plan

Changes from the originally planned statistical analysis specified in the protocol are outlined in [Table 1](#).

Table 1 Changes to Protocol Defined Analysis Plan

Protocol	Reporting & Analysis Plan	
Statistical Analysis Plan	Statistical Analysis Plan	Rationale for Changes
	
 An additional population has been defined, the Activity Monitoring (AM) Population, which will comprise all subjects in the ITT population who provide data from at least one activity monitoring session. 	
 Population needed for subset of subjects participating in Activity Monitoring.
	
 All other Endpoints promoted to secondary endpoints 	
 Study aims have developed since protocol and thus previous endpoints classed as 'other' have further importance
	
 An analysis by Maintenance Naive (MN) and Non-Maintenance Naive subgroups have been included. 	
 To investigate prospectively the 1st line use of LAMA/LABA in all symptomatic subjects (no existing data the literature to our knowledge)
	
 An analysis of ratio of trough FEV1 to baseline trough FEV1 	
 To investigate trough FEV1 ratio change from baseline

 Intent-to-treat ICS free (ITT ICS free) 	
 Population excluded. 	
 G-BA analysis to be conducted on the ITT population due to a change in G-BA guidance.

 To compare albuterol/salbutamol use captured in the eDiary with the electronic metered dose inhaler (eMDI) Device as data allow 	
 Not included in this RAP. 	
 Will be included in a supplementary RAP if deemed necessary.

Protocol	Reporting & Analysis Plan	
Statistical Analysis Plan	Statistical Analysis Plan	Rationale for Changes

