2.3. Study Design

Overview of Key Study Design Features	
Design Features:	
 • Multi-centre, randomized, double blind, double dummy, 3-arm parallel group study to compare Umeclidinium/Vilanterol, Umeclidinium, and Salmeterol in subjects with chronic obstructive pulmonary disease (COPD). • Approximately 3232 subjects will be screened, such that 2424 subjects will be randomized and approximately 2181 evaluable subjects complete the study. • Eligible subjects will be stratified by country, long-acting bronchodilator usage during the run-in (none or one long-acting bronchodilator per day) and activity subset (activity subset or no activity subset), and randomized in a ratio of 1:1:1 to UMEC/VI inhalation powder (62.5/25 mcg once daily) administered via the ELLIPTA inhaler, or UMEC (62.5 mcg once daily) administered via the ELLIPTA or salmeterol (50 mcg BID) administered via the DISKUS. Note the activity subset was only included as a randomisation stratification group for logistical purposes. • A subset of subjects up to 150 per treatment arm will undergo assessment of their physical activity measured through a physical activity monitor (Actigraph GT9X) worn for 7 days from Screening (Visit 1), for 7 days from Randomisation (Visit 2), 7 days from Visit 3, and for 7 days prior to last clinic Visit (Visit 5). • The total duration of subject participation in the study will be approximately 29 to 35 weeks consisting of 6 weeks pre-screening if necessary, 4 weeks run-in, 24 week treatment and one week Follow-Up.
Dosing :	
 • The following study medications will be used in this study: 
 - UMEC/VI 62.5/ 25mcg administered via ELLIPTA - UMEC 62.5 mcg administered via ELLIPTA - Salmeterol 50 mcg administered via DISKUS - Placebo via ELLIPTA - Placebo via DISKUS 
Subjects will be instructed to take one dose of medication each morning from the ELLIPTA (one inhalation equals one dose), and one dose in the morning and one in the evening from the DISKUS.
 
The ELLIPTA will provide a total of 30 doses and the DISKUS will provide a total of 60 doses.

Overview of Key Study Design Features	

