- Least squares (LS) mean and LS mean changes from baseline with their corresponding standard errors (SEs) will be presented for each treatment by visit, together with estimated treatment differences (UMEC/VI 62.5/25 vs. UMEC 62.5, UMEC/VI 62.5/25 vs Salmeterol and UMEC 62.5 vs Salmeterol), corresponding 95% CIs and p-values.
- A plot of LS mean changes from baseline and 95% CIs for each treatment by visit will be generated.
- A plot of LS mean treatment differences and 95% CIs between the treatment groups by visit will also be generated.
- The type III tests of fixed effects and the covariance parameter estimates from the model will be presented in two tables.

Summary Results Presentation

- Summary of baseline FEV₁ will be presented by treatment for all subjects.
- A box plot and an empirical distribution function plot of change from baseline in trough FEV₁ at Week 24 will be produced.
- Summary statistics for raw and change from baseline in trough FEV₁ at each visit and for each treatment will be presented on the same table.

Sensitivity and Support Statistical Analysis

- An assessment of whether the effect of treatment is modified by the interaction with
 - o Baseline FEV₁
 - o Geographical Region
 - o Stratum (no. of bronchodilators per day during run-in)
 will be made (for primary endpoint only for the ITT population only) by fitting separate MMRM models including an additional term for treatment by each covariate. The interaction term will be tested at the 10% significance level.
- For factors with two levels or continuous factors i.e. Baseline FEV₁ and Stratum, interactions with treatment will be investigated by fitting a model with the same terms as the main model, and adding in treatment by factor by Visit interaction. Contrast statements will be used to obtain the p-value for the treatment by factor interaction at Week 24. If that p-value is ≥ 0.10 the interaction will be considered not significant. If the p-value is < 0.10 , further investigation will be performed, for example running analysis by each level of the factor, or for subgroups

above and below the median.

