10.5.2. Study Population

Demographics
Age

 Since the eCRF only collects the year of birth, GSK standard IDSL algorithms will be used for calculating age where date and month will be imputed as '30th June'. Birth date will be presented in listings as 'YYYY'. Age will be calculated based on the Pre-screening visit date.
Age Category

 Age categories are based on age at Pre-screening and are defined as: 
 ≤64 years 65-74 years 75-84 years ≥85 years
Body Mass Index (BMI)

 Calculated as Weight (kg) / Height (m)²

Smoking Status

 Smoking status at Screening is determined directly from the eCRF.

Maintenance Naive/Non Maintenance Naive

 Maintenance naive (MN) is defined as subjects with no COPD maintenance medication apart from short-acting bronchodilators recorded in the 30 days prior to screening (evaluation period 30 days prior to screening until 1st study treatment).

Reversibility and GOLD Classifications
Reversibility

 • A subject's responsiveness to salbutamol at Screening will be classified as 'Reversible' or 'Non-reversible' based on the difference between their pre-salbutamol assessment of FEV₁ and their post-salbutamol assessment of FEV₁ as follows: 
 • Reversible, if they had a difference in FEV₁ of $\geq 12\%$ and ≥ 200 mL, or • Non-reversible, if they had a difference in FEV₁ of < 200 mL or a ≥ 200 mL difference that was $< 12\%$ of the pre-salbutamol FEV₁.
GOLD Grade 1-4

Based on the Global Initiative for Chronic Obstructive Lung Disease (GOLD, 2018), Subjects will be classified into GOLD Grades 1-4 using the post-salbutamol percent predicted FEV₁ assessment at Screening (Visit 1):
 
 • GOLD Grade 1 (Mild): Percent Predicted FEV₁ $\geq 80\%$ • GOLD Grade 2 (Moderate): $50\% \leq$ Percent Predicted FEV₁ $< 80\%$ • GOLD Grade 3 (Severe): $30\% \leq$ Percent Predicted FEV₁ $< 50\%$ • GOLD Grade 4 (Very Severe): Percent Predicted FEV₁ $< 30\%$
GOLD Category A-D (Using CAT)

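### The maintenance-naive subgroups are fitted separately with no treatment-by-subgroup contrast, and the definition of the subgroup gives two different end dates

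*SAP*

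**What the plan says.** Table 1 in SAP section 2.1 lists this among the changes from the protocol: "An analysis by Maintenance Naive (MN) and Non-Maintenance Naive subgroups have been included". The stated reason is to study first-line LAMA/LABA use in symptomatic subjects.

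Section 7.4 sets the method: "Analysis will be performed 'by' each subgroup separately", with the model taken over from the main analysis of each endpoint. Results are presented in the same form as in the main analysis. For trough FEV1 that means treatment differences with 95% CIs and p-values in each subgroup.

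Section 7.1.5.1 assesses effect modification by baseline FEV1, geographical region and run-in bronchodilator stratum, "by fitting separate MMRM models including an additional term for treatment by each covariate". It adds: "The interaction term will be tested at the 10% significance level". This applies to the primary endpoint only. Table 2.06 reports those three factors. MN status is not among them, and the MN display list under 10.8.10 has no interaction table.

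Section 10.5.2 defines MN as "no COPD maintenance medication apart from short-acting bronchodilators recorded in the 30 days prior to screening", and in the same sentence adds a bracket: "evaluation period 30 days prior to screening until 1st study treatment".

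**The concern.** Two separate defects affect the same subgroup.

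First, two separately fitted models give two treatment effects and two p-values but no estimate of how far the effects differ. Each subgroup is smaller than the whole trial, so with one common effect it is quite possible for one to be significant and the other not. A reader who sees both sets of results has no pre-specified quantity to correct that impression. For the three factors in 7.1.5.1 the SAP does the reverse: it tests the interaction first and looks within levels only if that test is positive. MN status, the one subgroup factor that the SAP itself added, goes straight to the within-level analysis.

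Second, the MN flag cannot be programmed without choosing between two end dates. The choice moves some subjects between subgroups, and it also affects whether the main model can be fitted as written in the MN subgroup.

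**Working it through.** **Scale.** The MN list under 10.8.10 contains 12 study population tables (1.33 to 1.44), 56 efficacy tables (2.78 to 2.133), 23 figures (2.48 to 2.70) and 9 safety tables (3.34 to 3.42): 12 + 56 + 23 + 9 = 100 displays. Of the 56 efficacy tables, 32 report a model or test (counting the exacerbation rate, Table 2.107). The other 24 are summaries.

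**Chance that exactly one subgroup is significant under a common effect.** The SAP gives no power, SD, effect size or MN share, so there is no planned figure to reproduce. Assumptions, none from the SAP: overall power P from 90% to 99%, MN share f from 20% to 50%, equal variances, and the same true effect in both subgroups. The two-sided 5% level is from section 2.4.

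- Overall standardised effect: ncp = 1.960 + z(P). This is 1.960 + 1.282 = 3.242 at 90% and 1.960 + 2.326 = 4.286 at 99%.
- Subgroup power: p1 = Φ(ncp·√f − 1.960) for MN and p2 = Φ(ncp·√(1−f) − 1.960) for non-MN. The opposite tail is negligible.
- Exactly one significant: p1(1−p2) + p2(1−p1).

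At P = 90%, f = 20%: p1 = Φ(1.450 − 1.960) = 0.305 and p2 = Φ(2.899 − 1.960) = 0.826, so the result is 0.305×0.174 + 0.826×0.695 = 0.627. At P = 99%, f = 50%: p1 = p2 = Φ(3.031 − 1.960) = 0.858, so the result is 2×0.858×0.142 = 0.244.

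| Overall power | f = 20% | f = 30% | f = 40% | f = 50% |
|---|---|---|---|---|
| 90% | 0.627 | 0.540 | 0.485 | 0.466 |
| 95% | 0.608 | 0.496 | 0.425 | 0.401 |
| 99% | 0.516 | 0.365 | 0.274 | 0.244 |

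An interaction test at the SAP's own level would wrongly declare a difference in 10% of such trials.

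**What the interaction contrast can deliver.** Its standard error is that of the overall comparison times √(1/f + 1/(1−f)) = 1/√(f(1−f)), which is 2.5 at f = 20% and 2.0 at f = 50%. If the subgroup effects differ by as much as the whole overall effect, the contrast has ncp·√(f(1−f)). At 90% overall power that is 3.242×0.4 = 1.297 or 3.242×0.5 = 1.621. Against the 10% critical value of 1.645, power is 37% and 49% respectively.

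**The two windows.** The first reading of 10.5.2 stops at screening; the bracket continues to first dose. Section 2.3 places between them the run-in of "4 weeks run-in, 24 week treatment and one week Follow-Up", so the end dates are about four weeks apart. A subject with no maintenance drug before screening and one recorded in the run-in is MN under the first reading and non-MN under the second. Under the second, every MN subject should fall in the stratum with no long-acting bronchodilator in the run-in. The stratum covariate is then constant in the MN model, which 7.4 takes over unchanged.

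**The case against.** The strongest reply is that Table 1 asks about first-line use. That calls for the effect within MN subjects, which a within-subgroup model with a CI supplies. This stands in part. A reader might infer that the sponsor intends to compare significance between subgroups or to claim a differential effect. The SAP says neither, and section 2.4 does not bring the subgroups into its testing procedure. The risk is a misreading that the plan leaves open, not one that it commits. But the SAP also analyses non-MN subjects, does not call the subgroup p-values descriptive, and gives no rule for reading one set of results against the other.

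The stratum interaction test overlaps with MN status. It is a partial proxy only: it concerns long-acting bronchodilators in the run-in, not all maintenance medication from 30 days before screening, and it covers trough FEV1 only.

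The bracket in 10.5.2 may be meant simply to state the period over which the rule applies. If so, the main clause needs rewording, because it names a shorter period. A reader might also infer from the one-bronchodilator stratum that subjects may start such a drug after screening. The document does not support that: the stratum records use during the run-in, and the rules on starting treatment lie in the protocol, which is not shown. The two readings differ for anyone with run-in medication only, but there may be few such subjects or none.

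Finally, interaction tests are weak. That is correct, and it is why an estimate with an interval is needed and not a p-value alone.

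**Conclusion.** Both defects hold, at moderate weight. The plan has no estimate of how the treatment effect differs between MN and non-MN subjects, and its MN definition can be programmed in two ways. The 24% to 63% range for discordant significance rests wholly on the assumed power, MN share and common effect. It shows that discordance would be unsurprising without any true difference; it does not predict this trial's result. It would be wrong to read all 100 MN displays as carrying p-values, since only the 32 modelled efficacy tables are at issue. The number of subjects affected by the window cannot be judged from the SAP. The primary comparison in the ITT population is untouched.

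**What to change.** 1. In 7.4, add MN status, treatment-by-MN and treatment-by-MN-by-visit terms to the full-population primary MMRM, following the method that 7.1.5.1 already gives for two-level factors. Report the Week 24 difference between subgroup effects with its 95% CI, and the interaction p-value at the SAP's 10% level, in Table 2.06. Rest any statement of differential effect on that estimate, say that a null test does not show equal effects, and label the within-subgroup p-values descriptive.

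2. In 10.5.2, state one MN window and use it for every MN display. If it runs to first dose, drop the stratum covariate from the MN-only models, where it is constant.

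While editing 7.4, correct its pointer to the displays: 10.8.8 holds the ICH listings, and the MN displays are under 10.8.10.

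The cost is one extra model, one row in an existing table and a few sentences. The drawback is low precision: the contrast has 2.0 to 2.5 times the standard error of the overall comparison, so the interval will be wide and often inconclusive.

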8. SAFETY ANALYSES

The safety analyses will be based on the ITT population, unless otherwise specified. Data collected after completion or withdrawal of study treatment will be considered post-treatment and included in relevant displays.

8.1. Adverse Events Analyses

Adverse events analyses including the analysis of adverse events (AEs), Serious (SAEs) and other significant AEs will be based on GSK Core Data Standards. The details of the planned displays are provided in [Appendix 8: List of Data Displays](#).

The 10 most frequent on-treatment adverse events in each treatment will be summarised. In case of ties in frequency all AEs for that frequency will be displayed. On-treatment AEs experienced by 3 % (without rounding) or more of subjects in any treatment group will also be displayed.

The most common on-treatment serious drug-related and most common on-treatment non-serious drug-related adverse events will be based on events experienced by 3% (without rounding) or more of subjects in any treatment group.

Classification of an AE as pre-, on- or post-treatment is provided in Section [10.3.2](#). All listings of AEs/SAEs will include an identification of the treatment phase (see Section [10.3.2](#)).

8.2. Adverse Events of Special Interest Analyses

Adverse events (AEs) of special interest (AESI) have been defined as AEs which have specified areas of interest for UMEC, VI or for the COPD population. A list of Standardized Medical Dictionary for Regulatory Affairs (MedDRA) Queries (SMQs) and other groupings for AESI is provided in Section [10.5.4](#).

Changes to the MedDRA dictionary may occur between the start of the study and the time of reporting and/or emerging data from on-going studies may highlight additional adverse events of special interest, therefore the list of terms to be used for each event of interest and the specific events of interest will be based on the safety review team (SRT) agreements in place at the time of reporting. The details of the planned displays are provided in [Appendix 8: List of Data Displays](#).

8.3. Clinical Laboratory Analyses

Laboratory evaluations for liver function tests will be based on GSK Core Data Standards. The details of the planned displays are in [Appendix 8: List of Data Displays](#).

10. APPENDICES

10.1. Appendix 1: Schedule of Activities

10.1.1. Protocol Defined Schedule of Events

			Blinded Treatment					
Visit	Pre-screen ¹ 0	Screen/ Run-in 1	Rando- mization 2	3	4	5	EW Visit ²	Telephone Follow up contact 6
Week	-10 to -4	-4	0	4	12	24		
Day	-70 to -28	-28	1	28	84	168		7 days after V5 or EW Visit
Window	-7/+2 days	-7/+2 days	-7/+2 days	-7/+2 days	-7/+2 days	-7/+2 days		±3 days
Screen/Baseline								
Informed consent	X							
Demography	X							
Medical/COPD history		X						
Smoking history/status		X						
Smoking cessation counselling		X						
Concomitant medication assessment	X	X	X	X	X	X	X	X
Height and weight		X						
Cardiovascular History/family history of premature CV disease)		X						
Screening spirometry (including post bronchodilator testing) ³		X						
CAT questionnaire		X	X					
Verify Inclusion/Exclusion Criteria		X						
Training on use of inhalers		X	X					
Training on use of eDiary and eMDI		X	X					
Verify randomization Criteria			X					

			Blinded Treatment					
Visit	Pre-screen ¹ 0	Screen/ Run-in 1	Rando- mization 2	3	4	5	EW Visit ²	Telephone Follow up contact 6
Week	-10 to -4	-4	0	4	12	24		
Day	-70 to -28	-28	1	28	84	168		7 days after V5 or EW Visit
Window	-7/+2 days	-7/+2 days	-7/+2 days	-7/+2 days	-7/+2 days	-7/+2 days		±3 days
Register Visit in InForm	X	X	X	X	X	X	X	X
Register Visit in RAMOS NG	X	X	X	X	X	X	X	X
Efficacy/HRQoL assessments								
Spirometry, including pre-dose FEV ₁ , trough FEV ₁ and inspiratory capacity			X	X	X	X		
SAC BDI questionnaire ⁴			X					
SAC TDI questionnaire ⁴				X	X	X		
SGRQ-C questionnaire ⁴			X	X	X	X		
CAT questionnaire ⁴		X	X	X	X	X		
EXACT/ER-S: COPD ⁵		—————→						
Patient Global Rating of COPD severity			X	X	X	X		
Patient Global Rating of Change in COPD				X	X	X		
Safety assessments								
Adverse events/Serious adverse events ⁶	X	X	X	X	X	X	X	X
COPD exacerbation assessment	X	X	X	X	X	X	X	X
12-Lead ECG		X						
Urine pregnancy test ⁷		X	X			X	X	
Pharmacogenetic sample ⁸			←———— X —————→					
Medication/Supplies								
Dispense rescue albuterol/slabutamol. Dispense MDI ⁹		X	X	X	X	X		
Assess COPD medication compliance ¹⁰ during run-in			X					
Dispense eDiary		X						
Assess compliance with eDiary during run-in			X					
Collect rescue albuterol/slabutamol.			X	X	X	X	X	

			Blinded Treatment					
Visit	Pre-screen ¹ 0	Screen/ Run-in 1	Rando- mization 2	3	4	5	EW Visit ²	Telephone Follow up contact 6
Week	-10 to -4	-4	0	4	12	24		
Day	-70 to -28	-28	1	28	84	168		7 days after V5 or EW Visit
Window	-7/+2 days	-7/+2 days	-7/+2 days	-7/+2 days	-7/+2 days	-7/+2 days		±3 days
Collect eDiary						X	X	
Dispense study treatment ¹¹			X	X	X			
Collect study treatment				X	X	X	X	
Assess study treatment compliance during treatment ¹⁰				X	X	X	X	
Study sub-set								
Physical activity monitor ¹²		X	X	X		X		
Collect Physical activity monitor						X	X	

1. Pre-screen Visit 0 must be completed prior to Screening Visit1. It can be completed 6 weeks prior or on the same day of V1, if no wash out of exclusionary medications is required.
2. Early Withdrawal Visit: Subjects that withdraw should return to the clinic as soon as possible to complete the Early Withdrawal Visit procedures.
3. Spirometry at screening should be performed as described in (Section 7.2.2.1 in the protocol).
4. SAC BDI, SAC TDI, SGRQ-C, CAT questionnaires will be completed at clinic visits and in the eDiary
5. EXACT/ER-S: COPD is completed daily in the eDiary approximately 2 hours before bed-time, starting on Day 1 of the run-in period.
6. For the start date of collecting AEs and SAEs see (Appendix 4)
7. Pregnancy test: for females for child bearing potential only.
8. Pharmacogenetic sample may be drawn at visit 2 or any visit after.
9. Rescue medication use to be recorded in the eDiary daily **and** in some sites in the eDiary and the eMDI
10. Sites are requested to call subjects every 2 weeks to remind them to take study treatment regularly and to record the time of the morning and evening dose in the eDiary.
11. In order to ensure subjects have sufficient doses of study treatment, they must return to clinic within 30 days from V2 and within 60 days from V3 respectively.
12. The Actigraph GT9X should be worn for 7 days from Visit 1, for 7 days from Visit 2, for 7 days from Visit 3 and for 7 days prior to Visit 5.

10.2. Appendix 2: Assessment Windows

10.2.1. Definitions of Assessment Windows for Analyses

Data are generally reported according to the nominal time of clinic visits and assessments as specified in the protocol, and time windows for exclusion will not be defined. For example, if a subject recorded values for the Week 4 (Day 28) visit that were actually made on the 21st day of treatment, they will be presented as Week 4 (Day 28) values in the summary tables.

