6.1.1. Disposition

The study population summary will show the number of subjects overall who were enrolled, the number of pre-screen failures, the number of screen failures and the number with each reason for screen failure, the number of run-in failures each reason the number with each reason for run-in failure and the number of subjects in each treatment group and overall who were randomized, in the ITT population. Of those in the ITT population the number and percentage of subjects in the AM population will be presented by treatment and overall.

The end of study record summary shows the number of subjects who completed the study as well as the number who withdrew early from the study along with reasons for early withdrawal.

The summary of study treatment status shows the number of subjects who completed study treatment as well as the number who stopped study treatment prior to the end of the study, along with the reasons for discontinuation.

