7.1.4. Strategy for Intercurrent (Post-Randomization) Events

An intercurrent event considered to have an impact on the estimand for the ITT population analysis is:

- Discontinuation of randomised treatment

- The primary treatment effect to be estimated for the ITT population will be the hypothetical effect if all subjects had stayed on their randomised treatment.

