7.1.5.1. Statistical Methodology Specification

Primary Statistical Analysis
Endpoint

 • Change from Baseline in trough FEV₁ at Week 24 (results for trough FEV₁ at all other time points and other treatment comparisons will be obtained from the same analysis even though those are not the primary endpoint)
Model Specification

 • Trough FEV₁ at Week 24 will be analysed for the ITT population using a mixed model repeated measures (MMRM) including data recorded at each of Week 4, Week 12 and Week 24. • The following covariates will be included in the model: baseline FEV₁, geographical region, stratum (no. of bronchodilators per day during run-in), visit, treatment, visit by baseline and visit by treatment interactions, where visit is nominal. • Two models will be fitted; one with a response variable of trough FEV₁, and one with a response variable of change from baseline in trough FEV₁. • While missing data are not explicitly imputed in the primary MMRM analyses, there is an underlying assumption that the data are missing at random. • The Kenward and Roger method (KR) for approximating the denominator degrees of freedom and correcting for bias in the estimated variance-covariance of the fixed effects will be used. • In the event the model fails to run using the KR method, then the residual method will be used instead. • An unstructured covariance structure for the R matrix will be used by specifying 'type='UN' on the REPEATED line. • Results for all time points where data are scheduled to be collected and all treatment comparisons will be included in the analysis and presented in the displays.
Model Checking & Diagnostics

 • Model assumptions will be applied but appropriate adjustments may be made based on the data.

Primary Statistical Analysis

- Normality assumptions underlying the model used for analysis will be examined by obtaining a normal probability plot of the residuals and a plot of the residuals versus the fitted values (i.e. checking the normality assumption and constant variance assumption of the model respectively) to gain confidence that the model assumptions are reasonable.
- If there are any departures from the distributional assumptions, alternative models will be explored using appropriately transformed data.

Model Results Presentation

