7.2.4. Strategy for Intercurrent (Post-Randomization) Events

All endpoints will use the same strategy for intercurrent events as defined in Section [7.1.4](#).

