
 For use of rescue medication endpoint, for a subject to be counted in a time period (except for baseline where at least 14 days non-missing entries required) they must have at least one diary entry recorded for that endpoint during that time period. For E-RS endpoint, for a subject to be counted in a time period they must have at least 16 days non-missing diary entries recorded for that endpoint during that time period. Any daily diary data that were collected post-study treatment discontinuation will be excluded from any analyses, including 4-weekly interval data summaries. 		

Calculation of Daily eDiary Endpoints
Use of Rescue Medication via E-diary

 The mean number of inhalations of rescue use per day and percentage of rescue-free days will be calculated during the 4-weekly interval intervals defined above.
EXACT PRO
EXACT Respiratory Symptoms

 The 4-weekly mean scores for E-RS, and the subscales RS-Breathlessness, RS-Cough and Sputum, and RS-Chest Symptoms will be calculated as the mean of the daily scores in the 4-weekly intervals defined above.
EXACT-RS and Subscale Scores Responder

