
For each four weekly period;
 
 A subject will be considered as a responder according to E-RS total score if their 4-weekly mean change from baseline EXACT-RS ≤ -2.0. A subject will be considered as a non-responder according to E-RS total score if their 4-weekly mean change from baseline EXACT-RS >-2.0. A subject will be considered as a responder according to RS-Breathlessness score if their 4-weekly mean change from baseline RS-Breathlessness ≤ -1.0. A subject will be considered as a non-responder according to RS-Breathlessness score if their 4-weekly mean change from baseline RS-Breathlessness >-1.0. A subject will be considered as a responder according to RS-Cough & Sputum score if their 4-weekly mean change from baseline RS-Cough & Sputum ≤ -0.70. A subject will be considered as a non-responder according to RS-Cough & Sputum score if their 4-weekly mean change from baseline RS-Cough & Sputum >-0.70. A subject will be considered as a responder according to RS-Chest Symptoms score if their 4-weekly mean change from baseline RS-Chest Symptoms ≤ -0.70. A subject will be considered as a non-responder according to RS-Chest Symptoms score if their 4-weekly mean change from baseline RS-Chest Symptoms >-0.70. Missing data will be handled as outlined in Section 10.6.2.

Rescue use for EMDI

- Will be analysed over Weeks 1 – 24 only
- The Medication Sensor Observation Period for each subject will be defined by the first date of sensor sync and the last date of sensor sync recorded in the database. Since a recorded rescue inhaler usage event in the database is also considered a sync event, if no first sync date is recorded, the date of the first rescue inhaler usage event will be used as the start date of observation. If no last sync date is recorded, the date of the last rescue inhaler usage event will be used as the end date of observation.
- A rescue occasion is defined as an inhaler usage event(s) in which one or more puffs occur within 2 minutes of each other, starting with the first reported puff.
- Days within the Medication Sensor Observation Period with no recorded rescue inhaler usage by the sensor will be assigned a rescue inhaler usage of 0.

Deterioration

- A Clinically Important Deterioration (CID) will be defined by a composite endpoint. A subject is considered to have deteriorated if, in the period from start of treatment to treatment stop + 1 day, one or more of the following occurs (definition dependent);

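### The SAP targets the effect under continued treatment but writes no on-treatment limit for clinic trough FEV1, FVC, IC and CAT values, although it has one for diary, exacerbation and CID data

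*SAP*

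**What the plan says.** **Target.** SAP 7.1.4 names discontinuation of randomised treatment as the intercurrent event and aims at "the hypothetical effect if all subjects had stayed on their randomised treatment". Section 7.2.4 adds: "All endpoints will use the same strategy for intercurrent events".

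**Data entering the primary model.** Section 7.1.5.1 fits an MMRM "including data recorded at each of Week 4, Week 12 and Week 24", with no condition on treatment status. FVC, IC and CAT follow the same method (7.2.5.1). Section 10.2.1 reports by nominal visit and says "time windows for exclusion will not be defined". Section 10.4.2 uses planned time relative to dosing for analyses and derived parameters unless stated otherwise.

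**Derivations (10.5.3).** Trough is built from readings 23 and 24 hours after the previous day's dose. The only exclusion written is for readings after the current day's dose. The CAT rule has no treatment-status condition. The SGRQ-C and BDI/TDI derivations are redacted.

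**Where a limit exists (10.5.3).** For the eDiary: "Any daily diary data that were collected post-study treatment discontinuation will be excluded from any analyses". Time to exacerbation runs to treatment stop + 1 day. CID, which uses the clinic FEV1, SGRQ, CAT and TDI values, counts a deterioration only "in the period from start of treatment to treatment stop + 1 day".

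**Disposition.** Section 6.1.1 summarises leaving the study and, separately, "the number who stopped study treatment prior to the end of the study". Tables 1.4 and 1.5 do the same.

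**The concern.** Under a hypothetical strategy for stopping treatment, a value observed after the stop is not an observation of the targeted quantity. It should be set aside and dealt with by the missing-data model. The SAP does this for three groups of endpoints and is silent for the group that contains the primary endpoint. If off-treatment clinic values exist and are kept, the Week 24 contrast mixes on- and off-treatment responses and no longer estimates what 7.1.4 states. The same reading would also be treated differently in two analyses in one report. For responders the choice can change the classification: an observed off-treatment value is scored as observed, whereas a missing value with no later assessment counts as non-response (10.6.2.3).

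**Working it through.** **1. Side-by-side reading**

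| Data | Limit written in the SAP |
|---|---|
| eDiary (rescue use, E-RS) | Post-discontinuation data excluded (10.5.3) |
| Exacerbations | Treatment stop + 1 day (10.5.3) |
| CID, including clinic FEV1, SGRQ, CAT, TDI | Treatment stop + 1 day (10.5.3) |
| Adverse events and log data | On-treatment phase to stop + 1 day (10.3.2) |
| Trough FEV1, FVC, IC in their own analyses | None explicit; a dose the day before is implied |
| CAT in its own analyses | None |
| SGRQ-C, TDI in their own analyses | Cannot be checked (redacted) |

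**2. A hypothetical record.** A subject stops on Day 150 and attends Visit 5 on Day 168.
- The reading is 168 − 150 = 18 days after the stop. The CID limit is Day 151, so the reading is outside CID.
- In the CAT analysis nothing removes it.
- In the FEV1 analysis the written exclusion cannot act, because there is no dose on the current day. The reading does not fit the trough description, since there was no dose on Day 167. However, 10.4.2 works from planned time, so no step checks the actual interval since the last dose.

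**3. The plan's own counts.** Section 2.3 gives 2424 randomised and about 2181 evaluable completers. 2424 − 2181 = 243, and 243/2424 = 10.0%. In reverse, 2181/(1 − 0.10) rounds up to 2424. The stated counts therefore reproduce with 10% non-completion.

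**4. Possible dilution.** Let f be the share of Week 24 values that are off treatment, equal in both arms, and r the fraction of the treatment difference they retain. Then

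estimated difference = [1 − f(1 − r)] × on-treatment difference.

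Neither f nor r is given in the SAP. The range for f is 0 (no one is assessed after stopping) to about 10% (every planned non-completer is assessed off drug, and completers are on treatment at Visit 5 as 10.6.1 requires).

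| f | r | Multiplier | Power if 80% planned | Power if 90% planned | Power if 95% planned |
|---|---|---|---|---|---|
| 0 | any | 1.00 | 80.0% | 90.0% | 95.0% |
| 2% | 0 | 0.98 | 78.4% | 88.8% | 94.2% |
| 5% | 0 | 0.95 | 75.9% | 86.9% | 92.8% |
| 10% | 0 | 0.90 | 71.3% | 83.1% | 90.0% |
| 10% | 0.5 | 0.95 | 75.9% | 86.9% | 92.8% |

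Power = Φ[(z₀.₉₇₅ + z_power) × multiplier − z₀.₉₇₅], with an unchanged standard error and two-sided 5%. The SAP states no planned power, so the 80%, 90% and 95% columns are assumptions. For f = 5%, r = 0 and 90%: (1.960 + 1.282) × 0.95 − 1.960 = 1.12, and Φ(1.12) = 86.9%.

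**The case against.** A reader might infer that off-drug values do enter the primary analysis. The SAP does not show this, and several passages point the other way.

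- **Trough definition.** It is tied to the previous day's dose, so a reading 18 days after the stop does not meet its wording. This stands as an implied limit for FEV1, FVC and IC. It is not a stated data rule, and it does nothing for CAT.
- **Early Withdrawal visit.** The schedule (10.1.1) marks no spirometry, TDI, SGRQ-C or CAT there. This closes one route. It does not cover a subject who stops treatment and still attends a scheduled visit.
- **Completion.** Section 10.6.1 requires treatment at Visit 5, which fits a design where stopping treatment ends participation. Section 10.5.1, however, defines a completer by the Visit 5 trough FEV1 assessment alone, and treatment stop is tabulated apart from study withdrawal. Separate tables do not prove that clinic testing continues off treatment, but they leave it open. The eDiary rule shows that at least diary entries after discontinuation are foreseen.
- **Section 10.2.1.** It concerns visit timing, and its example is an early on-treatment visit. It cannot be read as a decision to keep off-treatment values. The finding rests on 7.1.4, 7.1.5.1 and the trough and CAT rules, set against the eDiary and CID rules.
- **Section 8.** Its mention of data after study treatment concerns safety and says nothing about clinic efficacy values.

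Whether subjects stay in the study off treatment is for the protocol, which is not at hand. That limits what can be said about size. It does not supply the missing analysis rule.

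**Conclusion.** The gap is real. The SAP states a hypothetical estimand and enforces it for diary, exacerbation and CID data, but not explicitly for the visit-based MMRM and responder analyses of trough FEV1, FVC, IC and CAT. Read literally, a value dated after stop + 1 day is barred from CID and not barred from its own analysis. For SGRQ-C and TDI no conclusion is possible.

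The size is unknown and may be zero. With no residual effect the loss equals f, between 0 and about 10% at the planned non-completion. That range assumes equal shares in the arms. Unequal shares, or other therapy after stopping, could move a contrast in either direction, so a reader should not infer a demonstrated bias, including in the comparisons with salmeterol. The point should be settled before unblinding because it fixes which data enter the primary analysis. It does not show that the primary analysis is invalid.

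**What to change.** In 7.1.5.1 or 10.5.3, state that post-baseline clinic efficacy values dated after treatment stop date + 1 day are set to missing for the MMRM analyses. For responder analyses, handle them under 10.6.2.3, and do not count an excluded value as a later non-missing assessment. This reuses the cut-off already applied to CID and exacerbations. Keep the excluded values in listings. Check the unredacted SGRQ-C and BDI/TDI derivations and apply the same sentence if they lack one. If no such values are collected, saying so in the SAP would also close the point.

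The cost is one sentence and one derivation flag from dates already used for CID. The downside is a few more missing values, handled in the MMRM under the missing-at-random assumption it already makes. For responders, some observed values would become missing or non-response. This makes data use consistent, but scoring missing values as non-response is still not an estimate of response under continued treatment.
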